image; secondly, confirmation of precise probe placement in relation to the tumor is needed intra-procedurally; thirdly, the volumetric loss and peri-tumoral tissue inflammation promoted by the ablation limits the ability to evaluate with confidence the ablation margin intra-procedurally, therefore requiring a magnetic resonance (MR) or computed tomography (CT) study to be performed within 1-2 months following ablation procedure, a long period to evaluate the primary efficacy of this modality. Taking all together, those factors points to the need of having improved intra-procedurally imaging assessment of patients undergoing percutaneous ablation.

Currently, there are no commercially available tools that provide a robust and accurate method for tumor mapping and ablation confirmation that takes in consideration the biomechanical conformational changes promoted by this therapy. We hypothesize that local tumor control following percutaneous ablation of liver cancers will be significantly improved with the application of a dedicated anatomical linear elastic biomechanical model for treatment guidance and efficacy assessment by enabling the operator to accurately identify the tumor for ablation probe placement and assess intra-procedurally the minimal ablation margins, therefore increasing efficacy of percutaneous ablation therapy, ultimately improving liver progression-free survival rates.

Our preliminary data shows that our biomechanical model can accurately map the tumor, defined on pre-treatment computed tomography (CT) imaging, onto an intra-procedural CT image and is insensitive to imaging artifacts associated with ablation probe. We hypothesize that our innovative approach to modeling the tissue changes related to the ablation procedure will enable intra-procedure monitoring of the ablation

margin relative to the tumor. In addition, the combination of these technologies will provide further detailed information on the relationship between progression-free survival local tumor progression-free survival (LTPFS) and the ablation margins achieved.

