1.8 Method

RayStation® is a flexible, innovative treatment planning system. It combines unique features like unmatched adaptive therapy capabilities, multi-criteria optimization,

optimization for HDR brachytherapy and external beam therapy with photons, electrons, protons as well as helium and carbon ions. RayStation supports a wide range of treatment machines, providing one control center to create biomechanical deformable registrations using “Morpheus”. Morpheus lets the investigators focus all their skill and experience on evaluating and refining plan quality.

To investigate the impact of the proposed biomechanical model on clinical decisions during ablation guidance and end-point assessment, patients will be randomized in two treatment arms (i.e. experimental arm - including anatomical modeling of the liver, and control arm) with a 1:1 ratio. The primary objective is to assess whether applying biomechanical models during percutaneous ablation will increase the minimal ablation margins, which will be evaluated at the end of the procedure with the proposed software on both cohorts. Additionally, two other distinct end-points will be analyzed: ability of the model to provide tumor identification for ablation probe placement on intra-procedural non-contrast enhanced CT, and local tumor control rates achieved with the clinical application of this model. Operating physicians will be informed in respect which arm the patient was randomized at the time of ablation (figure 3).

[figure not shown]

Figure 3: Patient randomization flowchart

A. Impact on tumor targeting

The clinical trial will be designed according to the optimized parameters from our retrospective analysis. The optimized biomechanical models will be used to assess the accuracy (e.g. the ability of the model to accurately describe the motion, deformation, and volume change and tumor location in the liver between the pre-ablation contrast-enhanced CT and the intra-procedural non-contrast enhanced CT) in both cohort of patients. For the control arm, no information in respect tumor location and targeting will be provided for the operating physician during ablation. Imaging processing using the biomechanical model will be performed after procedure completion. For the experimental

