arm, tumor location and confirmation of appropriate targeting with ablation probe will be performed intra-procedurally utilizing the proposed software. Differences in tumor targeting accuracy between the two cohorts will be evaluated. If the accuracy of the cross validation cohort is not statistically significantly different, using a paired Student's T-test based on the preliminary retrospective results with significance defined as a p value of less than 0.05, from the initial optimization and validation results, then the model will be identified as complete. If the results are statistically worse, as an alternative approach, the initial cohort of patients will be used to perform an independent optimization of the model. Collaborations with the statistician will ensure that the appropriate power study has been performed for the analysis. The completion of this investigation will provide the accuracy of the present model in identifying and facilitate targeting of the liver tumors eligible for ablation when compared to the currently utilized standard of care tumor for tumor identification and targeting.

B. Impact on minimal ablation margins

A post ablation contrast-enhanced CT will be performed as per standard of care to assess the minimal ablation margins. Such assessment is currently performed manually using local rigid anatomic landmarks of the liver between the pre-ablation and post-ablation contrast-enhanced CTs. In this aim, we will evaluate the impact on the use of the advanced biomechanical model-based deformable alignment incorporating motion, deformation, and ablation-related volume loss in the liver between the pre-ablation contrast-enhanced CT and the post-ablation contrast-enhanced CT. The model will

automatically generate a minimal ablation margin on a three-dimensional Cartesian plan.

Such information will be utilized by the operator physician on the experimental arm to determine whether additional ablation is needed at a particular region surrounding the target tumor using a cut-off of at \geq 5 mm of minimal ablation margins in relation to the tumor borders in all planes (treatment arm). The \geq 5 mm minimal ablation margin will be used to account for the margin of error of the software, which is currently 3 mm. Frequency of total coverage of the target tumor, minimal ablation margins distance, and

[figure not shown]

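### The plan does not separate the experimental arm's primary margin from the software reading the operator re-ablated on, and does not mask the reader, so the margin gain may be overstated

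*Combined protocol and SAP*

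**What the plan says.** All quotes are from the combined protocol and SAP.

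- **Endpoint.** Section 1.8 Method says of the minimal margin, in both arms: "which will be evaluated at the end of the procedure with the proposed software on both cohorts". The Analysis Plan compares mean minimal margins between arms with a two-sample t-test or rank-sum test.
- **Experimental arm, targeting** (1.8, part A): "tumor location and confirmation of appropriate targeting with ablation probe will be performed intra-procedurally utilizing the proposed software".
- **Experimental arm, margin** (1.8, part B): "Such information will be utilized by the operator physician on the experimental arm to determine whether additional ablation is needed". The cut-off is 5 mm in all planes, chosen "to account for the margin of error of the software, which is currently 3 mm". The Procedure Details form has room for two re-ablation decisions.
- **Control arm** (1.8, part A, under targeting): "Imaging processing using the biomechanical model will be performed after procedure completion". The control operator receives no software information on location or targeting.
- **Images.** Targeting uses registration "between the pre-ablation contrast-enhanced CT and the intra-procedural non-contrast enhanced CT"; the margin uses registration "between the pre-ablation contrast-enhanced CT and the post-ablation contrast-enhanced CT". Both start from the pre-ablation contrast CT. Section 1.4 describes the model's ability to "map the tumor, defined on pre-treatment computed tomography (CT) imaging, onto an intra-procedural CT image".
- **Masking.** The Randomization section calls the trial open-label. No section names a masked or independent margin reader, or says that the experimental arm's endpoint is read again after treatment.

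**The concern.** The same instrument steers treatment and scores it, but only one arm is steered. An error common to both arms cancels in the difference of means. Error that decides when treatment stops does not cancel. A reading that is too high by chance passes 5 mm and stands; one that is too low leads to re-ablation and a new reading. If the last in-room reading is also the endpoint, this selection works in the experimental arm only.

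The arm difference would then mix true margin gain with retained reading error. The same comparison drives the interim rule that stops control enrollment at p < 0.003, so the source of the endpoint should be fixed in advance.

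The other planned outcomes would not settle the matter. Take 20 to 45 local recurrences per 100 patients, from the rates in 1.8, part C. A Cox comparison of arms then has 80% power only at a hazard ratio of exp(2 × 2.80/√events): about 3.5 at 20 events and 2.3 at 45. These are somewhat smaller once deaths are counted as events. The margin covariate in that model may itself be the in-room reading. A 45-day CT is scheduled, but no text ties it to margin scoring.

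**Working it through.** **1. The plan's own figure.** Inputs from Number of Participants: 50 per arm, difference 1.132 mm, SD 2, two-sided 0.05. The standard error is 2 × √(2/50) = 0.4, so the noncentrality is 1.132/0.4 = 2.83 on 98 degrees of freedom. The exact t-test power is 80.0%. The stated design is reproduced.

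**2. Bias if the acted-on reading is the endpoint.**

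From the documents: control readings with mean 2 and SD 2, the 5 mm cut-off, and up to two re-ablations (procedure form).

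Assumed:
- Error SD of 1.0 mm, or 1.53 mm (3/1.96, reading the stated 3 mm as a 95% limit; the plan does not say what it is).
- 0% or 50% of the error variance carried over between readings.
- True gain per re-ablation of 0 or 0.5 mm.

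Model: reading = true margin + error, with the true-margin SD set to √(4 − error SD²) so that readings keep SD 2. If a reading is below 5 mm, add the true gain and read again, at most twice. Bias = mean last reading − mean true margin. With 2,000,000 simulated patients, 93% of first readings fall below 5 mm.

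| Error SD | Carried over | Bias, no true gain | P(win) | Bias, 0.5 mm per round | P(win) |
|---|---|---|---|---|---|
| 1.0 | 50% | 0.05 | 3% | 0.07 | 69% |
| 1.0 | 0% | 0.11 | 4–5% | 0.14 | 73% |
| 1.53 | 50% | 0.13 | 5% | 0.16 | 74% |
| 1.53 | 0% | 0.28 | 10% | 0.34 | 84% |

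P(win) is the chance of a significant result favoring the experimental arm. Without bias it is 2.5% when there is no true gain. At 0.5 mm per round the true gain is about 0.90 mm and the unbiased P(win) is 61% to 64%. Against the design difference, 0.053/1.132 = 5% and 0.34/1.132 = 30%.

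**3. How far this depends on the model.**
- Error that is constant for a patient across all readings gives no bias in the mean.
- An error SD of 0.5 mm gives 0.03 to 0.06 mm for gains of 0 to 2 mm per round.
- At 1 to 2 mm of true gain per round, bias is 0.09 to 0.53 mm on a true gain of 1.74 to 3.25 mm.
- A model with the minimum taken over 6 or 12 directions, and local error that the operator corrects against and the endpoint retains, gives 0.05 to 1.27 mm for error SDs of 0.5 to 1.5 mm.

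So 0.34 mm is the top of the stated scenario, not an upper bound.

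**4. What a separate reading does.** If its error is independent of the in-room error, bias is 0.00 mm. If the two errors correlate 0.5, bias is halved, to 0.03 to 0.17 mm. Rerunning the software on reused contours could leave a correlation near 1 and remove little.

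**5. Error shared through the pre-ablation CT.** Assume a spherical ablation zone, equal-sized operator and software errors of mean 3-D size m, s = m/1.596, and probe scatter p = 1.5 mm per axis. Let ρ be the correlation between guiding and scoring error in each arm. With no true gain, the spurious difference is 1.596 × [√(2s²(1 − ρ control) + p²) − √(2s²(1 − ρ experimental) + p²)].

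For m from 1 to 3 mm:
- ρ 0.5 experimental, 0 control: 0.19 to 1.03 mm.
- ρ 0.5 experimental, 0.25 control: 0.09 to 0.55 mm.
- Equal ρ: zero.

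None of m, p or either ρ can be taken from the documents.

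**The case against.** **The plan never says that the in-room reading is the endpoint.** This is correct. A reader might infer that it is, but the text only places the evaluation at the end of the procedure with the software, which fits a later run as well. The point is that the plan permits the acted-on reading, not that it prescribes it.

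**Both arms use the same software, and the cut-off already allows for its error.** Common error does cancel. The 5 mm allowance, however, protects treatment. It does not separate the endpoint from the reading that guided it.

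**A win would still usually be real.** This largely stands. Selection at the cut-off seldom creates a false win, and where re-ablation adds 1 to 2 mm per round the conclusion is right and only the estimate is too large.

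**The software may be more accurate than assumed.** Section 1.5 reports mean distance to agreement of at most 1.0 mm for controlling structures, naming the liver, and changes of at most 0.8 mm from material-property or segmentation variability. Surface agreement is not target error, but it supports the lower part of the range.

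**A stronger reading is tempting:** that targeting error shared with the scoring run could by itself produce most of the design difference (1.03/1.132 = 91%). The documents do not support that. It needs a 3 mm mean error, an assumed correlation of 0.5, and no such correlation in controls. Yet part B of 1.8 describes current margin assessment as a manual comparison of pre- and post-ablation CTs, so error in defining the tumor on the pre-ablation CT could enter both arms.

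**Conclusion.** The point holds as a gap in how the primary endpoint is read. The plan allows an acted-on, unmasked reading in one arm to be compared with a reading that nobody acted on in the other. If the last in-room reading is the endpoint, the arm difference is inflated by about 0.05 to 0.34 mm (5% to 30% of 1.132 mm). That rests on assumed error SDs of 1.0 to 1.53 mm, error that varies between readings, and 0 to 0.5 mm of true gain per re-ablation. The main harm is an overstated estimate.

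A reader might go further and infer that a positive trial would be an artifact. The documents do not support that: with no true gain, a false win has a 3% to 10% chance, against 2.5%. Error shared through the pre-ablation CT is possible, but no figure should be put on it. This is a cheap improvement, and confidence is medium because the error inputs are assumed.

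**What to change.** Keep the software margin as the primary endpoint, and keep the 5 mm rule and the control arm. Add to 1.8 Method and to the Analysis Plan:

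*In both arms the primary margin is obtained after the procedure from the final post-ablation CT, with tumor and ablation-zone contours redrawn and the registration rerun by the staff who process the control images, following the same steps, with arm and any in-room reading or contour concealed. In-room readings guide care and are not the primary endpoint.*

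Also report in-room minus masked margin in the experimental arm, use the masked margin in the Cox model, and describe the result as a software-read margin. If the site already scores this way, writing it down closes the point.

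**Cost.** Re-contouring time and one software run for each experimental patient, about 60 (120/2). Control processing after the procedure is already planned. No patients or scans are added and care does not change. If the SD stays at 2 mm, 50 per arm still gives 80% power.

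**Limits.** Masked re-reading reduces shared error but does not eliminate it. Error from the common pre-ablation CT, or that the software repeats on the same images, would remain. Signs of repeat ablation on the final CT may hint at the arm.

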1.9 Collecting Time Points

Visit No.	Visit 1	Visit 2		Visit 3	Visit 4	Visit 5	Visit 6	Visit 7
Visit	Screening	Ablation day		45 days	3 months	6 months	1 year	2 years
Interval Window	Within 30 days ablation	Day 0 = ablation of target lesion		(± 14 days) postablation	3 months (± 1 month) postablation	6 months (± 1 month) postablation	12 months (± 1 month) postablation	24 months (± 3 months) postablation
Study Activity		pre	during	post				
Informed consent	x							
Demographic information	x							
Medical, surgical, radiation history	SOC							
BMI and ECOG performance	SOC	SOC		SOC	SOC	SOC	SOC	SOC
Child-Pugh, ASA scores, BCLC staging	SOC			SOC	SOC	SOC	SOC	SOC
CBC, Coagulation, liver function, renal tests	SOC			SOC	SOC	SOC	SOC	SOC
Alpha-fetoprotein	SOC			SOC	SOC	SOC	SOC	SOC
Carcinoembryonic antigen	SOC			SOC	SOC	SOC	SOC	SOC
Pregnancy test	SOC							
Inclusion/exclusion	x	x	x					
Concomitant medications	SOC	SOC		SOC	SOC	SOC	SOC	SOC
QOL questionnaire	x			x	x	x	x	x
Numeric Pain Rating Scale	SOC			SOC	SOC	SOC	SOC	SOC
CT scan	SOC	SOC	SOC	SOC	SOC	SOC	SOC	SOC
Ablation procedure information								
Liquid biopsy (ctDNA)		SOC		SOC		SOC	SOC	SOC
Physician assessment of software utility				x				
Device user experience				x				
Technical success assessment				SOC				
Technical efficacy assessment				SOC				
Follow-up postablation treatment				SOC	SOC	SOC	SOC	SOC

Legend: SOC: Standard of care (data collected as available per standard of care)

PROCEDURE TO OBTAIN CONSENT

The patients will be approached by either the Interventional Radiology Faculty or Research Staff, including research nurses and research coordinators. The principal investigator or designee who are licensed as physician in the state of Texas will obtain informed consent of participants prior to their procedure. During the consenting process patients will be educated and consented for their research participation in this study.

The study will follow the Office of Research SOP04 – Informed Consent Process.

PATIENT INFORMATION AND CONFIDENTIALITY PLAN

Confidentiality will be maintained throughout the study. An informed consent will be obtained prior to the percutaneous ablation procedure. No identifying information will

be used in any publication from this study. Patient identifiers will be available only to the investigators for the study and will be kept in a password-protected database and locked file cabinet. Unique patient identifiers will be used to replace patient name and medical record number. Paper records (data forms, list of patient names and unique identifiers), will be kept in a locked file cabinet with access granted only to study investigators. In the conclusion of the study, patient identifiers will only be maintained with the principal investigator to allow future review of the research. The protected health information used in this study will not be reused, nor will it be used for other research. As this is a prospective study, an informed consent will be obtained and authorization to use and disclose protected health information is requested.

Morfeus, a software-aided imaging application, is located within MD Anderson password protected behind the institutional firewall with access only granted to authorized study investigators. Morfeus will be provided at no cost to the study participants. There is no foreseeable injury or risk to subjects using Morfeus. Participants may withdraw from the study at any time for any reason and are not obligated to reveal their reasons for withdrawal, the data and test results already collected will be kept and may be used. All study data will be stored in password-protected computers and/or locked file cabinets and will continue to be stored securely after the study.

STATISTICAL CONSIDERATIONS

Statistical Design

The primary endpoint is to assess whether applying biomechanical models

increase the minimal margins of ablated lesions properly covered by ablation on a three-dimensional analysis. The secondary endpoints of our study will compare the two arms in respect local and systemic oncological outcomes following liver ablation, procedure-related complications, and quality of life via a quality of life (QOL) questionnaire. Specifically, we will analyze the 2-years local tumor progression free-survival rates at the ablated lesions. On the experimental arm, we will evaluate the impact of software use on procedure workflow as well user's experience.

Statistical Methods

A. Analysis Plan

Statistical analysis of this study will be the responsibility of the principal investigator (PI) and statistician. The PI and statistician will also be responsible for the appropriate conduct of an internal review for the final dataset and any study-related material to be authorized for publication.

To assess the effect of applying biomechanical image registration models during percutaneous microwave ablation, the primary endpoint of this intent-to-treat randomized trial will be on the impact of the software use on the minimal margins of ablated lesions properly covered by ablation on a three-dimensional analysis. Patients will be evenly randomized (i.e., 1:1 ratio) to two treatment arms (i.e. experimental arm - including anatomical modeling of the liver, and control arm) using the Pocock-Simon dynamic allocation method to balance the baseline covariates: tumor histology

(colorectal vs other histologies), RAS mutation (for colorectal only, yes vs. no vs.

undetermined), lesion size (<2cm, 2.0-3.0cm, >3cm-<5cm), subcapsular location, defined as tumor within 1 cm from the liver capsule (yes vs no) and presence of multiple lesions (yes vs. no). At the end of the study, the average minimum ablation margins will be compared between two arms using a 2-sample t-test (or Wilcoxon rank-sum test). The means and corresponding 95% confidence intervals will be reported for both arms of the study.

As a secondary objective, the Kaplan-Meier method will be used to estimate local tumor progression-free survival (LTPFS) and 95% confidence intervals for the quantiles of the LTPFS function based on the method of Brookmeyer and Crowley will be calculate for each arm. Time point probabilities (e.g., 2-year LTPFS) and the associated log-log transformed pointwise 95% confidence will also be reported. A multivariate Cox-proportional hazards model will be fitted to the data with ablative margin as a continuous variable to assess the significance of study arm and ablative margin size on LTPFS while simultaneously adjusting for known covariates that effect LTPFS. LTPFS will be measured from date of ablation to earliest date of progression at the ablated lesion, death. Those progression free and alive will be censored at their date of last clinic visit. Similar analysis will be used for 2-years intra-hepatic (progression at any site of the liver) progression-free survival and overall survival. Standard summary statistics will be computed for complication rates, quality of life, and liver function and compared between arms. Statistical significance will be defined as $p < 0.05$.

B. Randomization

A dynamic randomization method by Pocock and Simon will be used with a minimization probability parameter of 0.90. The randomization process will be controlled to ensure a balanced stratification by treatment arm for the factors listed above. Patients will be randomized to either experimental arm or no control arm using the Clinical Trial Conduct (CTC) website (<https://biostatistics.mdanderson.org/ClinicalTrialConduct>), which is housed on a secure server at MDACC and maintained by the MDACC Department of Biostatistics. Access to the website will be gained through usernames and passwords provided by the MDACC Department of Biostatistics to the clinical team. Training on the use of the CTC website to randomize patients on the study will be provided by the biostatistical collaborators. This is an open-label trial with stratified randomization. When a patient is enrolled on the study, the research nurse or coordinator of the study will enter patient's information including medical record number and stratification factors. Through the web interface, after the randomization button is clicked, the result of the randomization will be displayed on the screen for users to view. All data on randomization will be stored in a secure SQL server database.

PROTOCOL MONITORING PLAN

MD Anderson's Data Safety Monitoring Board (DSMB) will monitor the conduct of the study. The principal investigator will be responsible for the management of the protocol. Identifiers (name, medical record number) will be collected but will be replaced by study numbers in the analytical file. They key linking these numbers will be retained in a locked file by the principal investigator. All study personnel have

completed training in methods of maintaining the confidentiality of health information.

Electronic records will be stored on password protected institution computers behind the institution firewall. Only the principal investigator and research staff in Interventional Radiology will have access to the study. Data will not be transferred to laptop computers that are removed from the institution. Complete confidentiality will be maintained during this evaluation, manuscript preparation and submission. Information from individual Case Report Forms (CRFs) will be saved in an institutionally-based and approved electronic database. Adverse events such as inaccurate tumor localization and ablation coverage, as well as subsequent local tumor progression will be captured and recorded in OnCore.

DATA COLLECTION PLAN

All subjects will be registered in OnCore and data will be entered in an UT MD Anderson Cancer Center approved electronic database. The institutionally approved database is a secure, web-based application with controlled access designed to support data capture for research studies, providing: 1) an intuitive interface for validated data entry; 2) audit trails for tracking data manipulation and export procedures; 3) automated export procedures for seamless downloads to common statistical packages; and 4) procedures for importing data from external sources. It is hosted on a secure server by MD Anderson Cancer Center that has undergone an annual Governance Risk & Compliance Assessment by MD Anderson's Information Security Office and found to be compliant with HIPAA, Texas Administrative Codes 202-203, University of Texas Policy

165, federal regulations outlined in 21CFR Part 11, and UTMDACC Institutional Policy

#ADM0335.

Those having access to the data include the study PI and research team personnel. Users are authenticated against MDACC's Active Directory system. The application is accessed through Secure Socket Layer (SSL). All personal identifying information will be removed from the data when it is exported for analysis.

Following publication, study data will be archived in the electronic database indefinitely, since study data may be useful for future research studies performed under separate IRB approved protocols. Since this is a secure electronic database with controlled access, and because subject identifiers may be needed to link study data to data from other sources under future IRB approved protocols, subject identifying information will be retained in the archived database. No specific subject identifiers will be collected in this study. We acknowledge that there is a theoretical chance that the participants may be identified from their combined responses to the demographic questions. However, no attempt will be made by the research personnel to identify the survey respondents. Also, data will only be reported in aggregate form. The demographic information in the survey, along with all other survey responses, will be stored securely in the database. Up to five fully deidentified CT images will be shared with RaySearch Laboratories for joint development purposes directly related to the NIH-funded Academic-Industry Partnership R01 for the COVER-ALL clinical trial and project. RaySearch Laboratories is the industry partner for this grant.

REFERENCES

